Power Analysis Considerations. Mixed effect analyses will be used to examine the effects of CBT-I on the developmental trajectories of the primary outcomes of interest; insomnia, depression, PTSD, and SI severity. Here, the power approach for longitudinal mixed effects models put forth by Hedeker, et al. was used. This tests for the statistical power to detect change over time (i.e., slope) using a random effects model (both slope and intercept). For the current proposal, necessary estimates were supplied via pilot results examining unconditional change in SI, depression, PTSD, and insomnia. In all instances, we are interested in the effect of CBT-I on the linear slope (the five time points after the intercept time point) using a two-sided alpha of .05 and .80 power, a 1:1 group ratio, no correlation between intercept and slope, and no correlated residual variance. Higher correlations between intercept and slope and among residual variance both serve to increase power estimates. To help improve power to detect change, two additional data collection time points have been added to this revised proposal. For the outcomes of SI, depression, and insomnia severity, pre-post (6 weeks) standardized effect sizes from the pilot study were all positive and exceeded .40. For power simulations, we tested for linear change from baseline through 6 month follow-up (time points 0, 6, 12, 18, 24 and 30 weeks), testing for the power to detect an effect size of .4 at the 30 week (6 month follow-up) time point. A 20% attrition rate was incorporated into the model, assuming a typical longitudinal attrition pattern with most participants lost early (7% at post-treatment and 5%, 3%, 3%, and 2% at subsequent assessments, respectively). Remaining estimates were supplied via pilot results examining unconditional change in SI, insomnia, depression, and PTSD. For the main outcome of SI, pilot data using the C-SSRS suggests an intercept variance of 10, slope variance of 1.2, and residual variance (error variance) of 24. With these estimates, 240 participants are required to achieve .80 power. Fewer participants are required to achieve .80 power to detect linear change for the remaining outcomes (N = 223 for depression, N = 222, for insomnia, and N= 184 for PTSD) with intercept, slope and residual variances based on pilot data.

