Missing Data. Mixed effects models and SEM incorporating full-information maximum likelihood make efficient use of all available data; we will also conduct analyses using multiple imputation of missing data as a form of sensitivity analysis. Multiple imputation uses a regression based approach to impute values for data that are missing, providing that data meets the missing at random criteria. To improve estimates, the procedures put forth by Allison regarding intervention studies will be followed. Here, each treatment condition is imputed separately and resulting datasets are merged. Following Rubin, ten imputations will be performed and each resulting datasets will be analyzed as above. The results obtained will be combined following the techniques employed by Rubin. Multiple imputation has consistently demonstrated less biased parameter estimates than most other traditional approaches to the handling of missing data. If missingness appears biased by treatment condition, a pattern-mixture approach to missing data will be assessed. Here, different patterns of missingness are identified and participants are placed into groups based on their missingness pattern. Dummy variables representing group membership are entered into the mixed effect and SEM analyses; intervention by group membership interaction terms are assessed to examine for differential effects on outcomes dependent on missing data patterns.

The SEM to be tested will make use of the full-information maximum likelihood estimation method, which uses estimates throughout the model to provide more accurate estimates where data is missing. Again, this approach provides more realistic parameter estimates than other missing data techniques when data is missing at random or missing completely at random.

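### Ten imputations leave about 0.10 to 0.12 standard errors of seed-to-seed noise, so a borderline sensitivity result can change sides; 50 to 100 imputations would reduce this cheaply

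*Combined protocol and SAP*

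**What the plan says.** The Missing Data section makes likelihood the main approach: mixed models, and structural equation models (SEM) with full-information maximum likelihood, on all available data. Multiple imputation is secondary: "we will also conduct analyses using multiple imputation of missing data as a form of sensitivity analysis". Imputation is by arm ("each treatment condition is imputed separately and resulting datasets are merged"), the count is fixed ("ten imputations will be performed and each resulting datasets will be analyzed as above"), and results are pooled by Rubin's rules. The count rests on a citation. The section gives no seed, no Monte Carlo error, and no rule for a disagreement between the imputed and the likelihood results.

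Power Analysis Considerations supplies the figures needed to size the noise. "A 20% attrition rate was incorporated into the model", lost as 7%, 5%, 3%, 3% and 2% over the five follow-ups. For SI, "pilot data using the C-SSRS suggests an intercept variance of 10, slope variance of 1.2, and residual variance (error variance) of 24".

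Two other sections matter. Type 1 Error Protection adjusts the multiple comparisons by Benjamini-Hochberg. The Aim 2 analysis judges indirect effects by whether 95% limits contain zero.

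**The concern.** A sensitivity analysis is read by comparison: does the imputed result agree with the likelihood result? The likelihood result carries no imputation noise. The pooled result does, because a different seed gives a different estimate and standard error from the same trial data. If that noise is large relative to the distance from the cut-off, agreement or disagreement on significance may reflect the seed and not the handling of missing data. Without a prespecified seed, the p-value that will be reported is not fixed by the plan.

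What is at stake is the reproducibility of a secondary check, not the main test of any aim.

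**Working it through.** **Inputs (Power Analysis Considerations).** SI variances: intercept 10, slope 1.2, residual 24. Visits: "time points 0, 6, 12, 18, 24 and 30 weeks". Retention from the stated losses: 1, .93, .88, .85, .82, .80. Effect: .4 SD at week 30. Test: two-sided .05, power .80, 1:1. The time unit of the slope variance is not stated, so three were tried.

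**1. Reproduce the plan's sample size.** For a linear contrast c with attrition, N per arm = 2(1.960 + 0.842)² × Σ cᵢcⱼSᵢⱼ/√(rᵢrⱼ) ÷ (c′μ)², where S = 10 + 1.2tt′ + 24I, r is retention, and μ rises linearly to .4 SD at week 30. With time in 6-week visits, the week-30 SD is √(10 + 1.2×25 + 24) = 8, the difference is 3.2, and total N is 236. With time in months it is 240, and in weeks 246. The plan states 240, so these inputs are a fair reading of it.

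**2. Missing information for the slope.** FMI = 1 − V(complete)/V(observed). V(complete) = 1.2 + 24/Σ(t − t̄)². V(observed) comes from the information summed over the dropout patterns.

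| Time unit | V(complete) | V(observed) | FMI |
|---|---|---|---|
| Visit | 1.2 + 24/17.5 = 2.571 | 3.031 | .152 |
| Month | 1.2 + 24/39.375 = 1.810 | 2.125 | .149 |
| Week | 1.2 + 24/630 = 1.238 | 1.375 | .100 |

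Sixty simulated trials of 240, imputed by arm with sequential regressions, gave a mean FMI of .165.

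**3. Noise in the pooled estimate.** The seed-to-seed SD is √(FMI/m) standard errors.
- m = 10: √(.10/10) = 0.100 and √(.15/10) = 0.122.
- m = 50 at FMI .15: 0.055. m = 100: 0.039.
- Relative efficiency at m = 10 and FMI .15: 1/(1 + .15/10) = .985.

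**4. Effect on the p-value.** The pooled estimate and between-imputation variance were drawn repeatedly and referred to a t distribution with multiple-imputation degrees of freedom. The share of runs with p above .05 when the noise-free p is .04 was:

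| FMI | m = 10 | m = 50 | m = 100 |
|---|---|---|---|
| .10 | 23% | 3% | under 1% |
| .15 | 30% | 7–8% | 2% |
| .30 (assumed upper case) | 41% | about 20% | 10% |

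At FMI .15 and m = 10, about 10% of runs cross from a noise-free p of .03 and about 12% from .07, falling to about 2% from .09. For an observed-data p of about .05, 95% of seeds give .027 to .096 with ten imputations, .038 to .067 with fifty and .041 to .061 with one hundred.

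**5. How often it would matter.** In a trial with the planned 80% power and FMI .15, two seeds disagree at .05 in 4.8% of trials with ten imputations, 2.0% with fifty and 1.4% with one hundred. At the design point itself (z about 2.8, p about .005), ten imputations give p from .002 to .013, with essentially no runs above .05.

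**The case against.** The case for leaving ten alone is respectable. Ten is a cited choice and loses only about 1.5% efficiency. Multiple imputation is a sensitivity analysis with no decision rule attached, so crossing .05 changes no stated conclusion. Such an analysis is best read by comparing estimates and intervals, and on that scale 0.12 standard errors is small. Benjamini-Hochberg means that .05 is not always the cut-off. The documents give no FMI, and the data-analysis section counts time in weeks, which gives the lower value of .10.

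Most of this stands, and it limits the point to borderline results. It does not remove it. The same noise applies at whatever cut-off the adjustment produces. The imputed datasets go through the same analyses as the main ones, including the confidence-limit rule for indirect effects, so readers will compare significance as well as estimates. At the lower FMI of .10, a noise-free p of .04 still exceeds .05 in 23% of runs with ten imputations.

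A reader might infer that fifty imputations settle the matter. They do not: fifty cuts the noise by √5 = 2.24, and at FMI .15 a noise-free p of about .04 to .065 can still change sides. A reader might also infer that the trial's main findings depend on the seed. The documents do not support that, because the mixed models and full-information SEM use no imputation.

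**Conclusion.** The point holds as a minor, cheap improvement. With the plan's own attrition and SI variances, ten imputations leave about 0.10 to 0.12 standard errors of seed noise in the slope difference. A sensitivity result with a noise-free p of roughly .03 to .09 may then fall on either side of the cut-off by seed. Clear results are stable.

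It would be wrong to read this as a mistake in the plan: ten is adequate for average efficiency, and nothing in the documents contradicts it.

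The size rests on three assumptions: dropout at random and equal in both arms, SI variances as stated from the C-SSRS pilot although the outcome is now the SSI, and an unstated time unit. The upper case of .30 allows for extra missingness, for example in sleep diaries. It is an assumption and not a figure from the plan.

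**What to change.** In the Missing Data section, replace ten imputations by at least 50, preferably 100, with a prespecified seed. Report the Monte Carlo error of the pooled estimate beside each imputed result. Keep imputation by arm and the same combining rules.

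This reduces seed dependence without eliminating it, so the reported Monte Carlo error is what tells the reader whether a borderline result is stable. The cost is a short change to the text and five to ten times the model fits, including the SEM with bias-corrected limits. That is computing time only: no participants, visits or measurements change.

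### For suicidal ideation, the plan commits to no analysis that departs from missing at random: the imputation labelled a sensitivity analysis shares the main model's assumption, and the pattern-mixture model depends on an undefined trigger

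*Combined protocol and SAP*

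**What the plan says.** The Missing Data paragraph of the Data Analysis section has three elements.

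- **Main analyses.** Mixed-effects models and a structural equation model fitted by full-information maximum likelihood use all available data. For the structural equation model, the text limits the claimed advantage to data missing at random or completely at random.
- **Multiple imputation, always run.** "we will also conduct analyses using multiple imputation of missing data as a form of sensitivity analysis". Ten imputations are made, each arm separately. The stated condition is "providing that data meets the missing at random criteria".
- **Pattern-mixture model, conditional.** "If missingness appears biased by treatment condition, a pattern-mixture approach to missing data will be assessed". Dummy variables for the missingness pattern, and their interactions with treatment, would enter the models. No test, threshold or timing defines the condition.

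Two other places touch on the subject. General Considerations checks baseline balance. The Data Safety Monitoring Board section has attrition biases reported to the board. Neither is an analysis under an assumption other than MAR, and none appears elsewhere in the document.

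**The concern.** A sensitivity analysis is useful when it changes the assumption in doubt. Here the doubtful assumption is MAR: given what was observed, dropout does not depend on the unseen outcome. The mixed model needs it because it is likelihood-based, and the imputation needs it by the plan's own statement. Imputing each arm separately allows different regressions by arm but is still MAR within arm. If the two analyses agree, that says nothing about MAR.

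The one analysis that could relax MAR may never be run. Bias in the treatment contrast depends on why people leave and on how their unseen outcomes differ between arms. Similar dropout rates do not rule that out. Different reasons are plausible, because CBT-I asks for sleep restriction and stimulus control while SH is education and goal setting.

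At stake is Hypothesis 1d. A team that follows the plan exactly could report the SI effect as robust on the strength of two analyses that rest on one assumption.

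**Working it through.** **Inputs, all from Power Analysis Considerations**
- Design: "using a two-sided alpha of .05 and .80 power, a 1:1 group ratio".
- Effect: "testing for the power to detect an effect size of .4 at the 30 week (6 month follow-up) time point".
- Variances: "pilot data using the C-SSRS suggests an intercept variance of 10, slope variance of 1.2, and residual variance (error variance) of 24".
- Visits: "time points 0, 6, 12, 18, 24 and 30 weeks".
- Loss: "A 20% attrition rate was incorporated into the model", split 7%, 5%, 3%, 3% and 2%. Retention is therefore 1, .93, .88, .85, .82 and .80.

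The time unit of the slope variance is not given. I assume 6-week visits, coded 0 to 5.

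**Step 1: reproduce the plan's N.** The method the plan cites for longitudinal contrasts gives n per arm = 2(z.975 + z.80)² c'Vc / (c'μ)². Here c is the linear contrast, V is built from the three variances, and each visit is weighted by its retention. With the standardised effect rising linearly from 0 to 0.4, c'Vc = 938.25 and c'μ = 11.094. Total N = 4 × 7.849 × 938.25 / 11.094² = 239.3, which is the plan's 240. A raw difference rising linearly gives 234.8, and the mixed-model information matrix gives 234. The assumed time unit is therefore consistent with the stated N.

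**Step 2: scale.**
- Week-30 SD = √(10 + 25 × 1.2 + 24) = √64 = 8.0.
- Planned difference = 0.4 × 8.0 = 3.2 points.
- Residual SD = √24 = 4.9.
- Standard error of the slope difference at N = 240, from the information matrix = 0.2247 per visit, so expected z = (3.2/5)/0.2247 = 2.85 and power is .81.

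**Step 3: delta adjustment with equal 20% dropout.** Suppose CBT-I dropouts are worse than MAR predicts by δ and SH dropouts are not. The week-30 difference is then 3.2 − 0.20δ.

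| δ (points) | Delta-adjusted difference | Planned MAR analysis reports | Power of the delta-adjusted test |
|---|---|---|---|
| 0 | 3.2 | 3.2 | .81 |
| 1.6 | 2.88 | about 3.2 | .73 |
| 3.2 | 2.56 | about 3.2 | .63 |
| 4.9 | 2.22 | about 3.2 | .51 |

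The last column describes a test the plan does not run. The cost to the plan as written is the gap between the second and third columns.

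**Step 4: where the conclusion tips at the planned effect.** With the standard error held fixed, the significance limit is 1.96 × 5 × 0.2247 = 2.20 points. It is reached at δ = (3.2 − 2.20)/0.20 = 5.0 points, just over one residual SD. A grid that stops at one residual SD could therefore stop just short of the tipping point.

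**Step 5: bias of the MAR mixed model.** A simulation used N = 240, 4,000 runs, equal dropout counts by arm and known variances. Dropout depended on the current unseen value. Its strength (log relative weight per SD: 1 moderate, 2 strong) is an assumption and does not come from the documents.

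| Dropout mechanism | Mean estimate, true effect 0.40 | Two-sided type I error, true effect 0 |
|---|---|---|
| Ignorable | 0.41 | .05 |
| Same in both arms (moderate) | 0.40 | .05 |
| CBT-I only, moderate / strong | 0.46 / 0.50 | .06 / .11 |
| SH only, moderate / strong | 0.34 / 0.30 | .07 / .10 |
| Opposite directions | 0.29 or 0.51 | .13 |

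Bias appears only where the mechanism differs between arms.

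**The case against.** **The trigger can be read broadly.** A reader might infer that the trigger compares dropout rates and so would not fire when rates are equal. The text names neither rates nor a test. If CBT-I patients left for reasons related to ideation and SH patients did not, that is missingness biased by condition on an ordinary reading. This objection stands against saying that the plan tests the wrong condition. It does not remove the gap: the plan does not commit to the broad reading, and the decision is left until the data have been seen.

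**Informative dropout need not bias the contrast.** This stands. The same mechanism in both arms left the estimate at 0.40.

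**Worsening before dropout may be compatible with MAR.** This stands too. The SSI is measured at six time points, and the treatment sessions collect a PHQ-9 ideation item, though the plan does not say that item will be used in imputation. Leaving after recorded worsening is something the mixed model can handle. The concern is limited to what remains unobserved.

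**The illustration is not on the outcome scale.** Correct. The variances are from the C-SSRS and the primary SI measure is the SSI-C, so the points are not SSI points. A reader might also take the falling power as a loss in the planned analysis. It is not, because that analysis keeps its nominal power of about .81 for an estimate that may be biased.

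**Pilot attrition was only 7.4%.** The protocol itself notes that the pilot had no longer-term follow-up, and this trial plans for 20%.

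**Conclusion.** The point holds in a limited form. For SI the plan commits to no analysis outside MAR, and the trigger for the one that might go further is undefined. Agreement between the mixed model and the imputation cannot be offered as evidence of robustness. The documents do not show that the trigger would fail to fire, or that the SI result will be biased.

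In the illustration, the planned analysis overstates the week-30 difference by 0.3 to 1.0 points out of 3.2 for δ from 1.6 to 4.9. Under the simulated mechanisms that differ by arm, an effect of 0.40 is estimated at between 0.29 and 0.51. These sizes rest on the C-SSRS pilot variances, a per-visit time unit, equal 20% dropout, and assumed values of δ and dropout strength. The main analysis can stay as it is. This is an inexpensive improvement that should be made before the data are analysed.

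**What to change.** 1. For Hypothesis 1d (SSI), extend the planned by-arm multiple imputation with a prespecified delta-adjusted tipping-point analysis. Worsen the imputed CBT-I values in steps from 0, which is the plain MAR run, to one residual SD of the SSI, and go further if the conclusion has not changed. Vary δ in the SH arm as well. Report the δ at which the conclusion changes.
2. Run the pattern-mixture model whether or not missingness looks different by arm, as supportive only. It cannot carry the point alone: 7 of the 20 percentage points of planned loss (35% of dropouts) occur at post-treatment. If those participants do not return, they have only a baseline value and their slope cannot be estimated without a further assumption. State that assumption.
3. Describe the plain imputation as a check on the handling of missing data under MAR, not as a test of MAR.

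The cost is a little more analysis time and one more result to report. No new data, visits or participants are needed.

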### **Specific Aims**

**Aim 1: To test the direct effects of a brief CBT-I intervention, compared to SH, on the trajectories of severity of insomnia, depression, PTSD and SI through 6 month follow-up.**

**Hypothesis 1a:** CBT-I, compared to SH, will be associated with a greater rate of reduction in severity of insomnia over time.

**Hypothesis 1b:** CBT-I, compared to SH, will be associated with a greater rate of reduction in depression severity over time.

**Hypothesis 1c:** CBT-I, compared to SH, will be associated with a greater rate of reduction in PTSD severity over time.

**Hypothesis 1d:** CBT-I, compared to SH, will be associated with a greater rate of reduction in SI severity over time.

**Aim 2: Utilize structured equation modeling to determine if (and how) effects of CBT-I on SI are mediated by sleep, by depression and by PTSD.**

**Hypothesis 2a:** CBT-I effects on SI at 6 months will be both direct and indirect, mediated by direct intervention effects on sleep, depression, and PTSD.

**Hypothesis 2b:** Depression at 3 months will be positively related to SI at 6 months.

**Hypothesis 2c:** PTSD at 3 months will be positively related to SI at 6 months.

**Hypothesis 2d:** Post-intervention sleep will be positively associated with 3 month depression, 3 month PTSD, and 6 month SI.

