For the main SI outcome, power likely improves with the change to the SSI as we suspect that more variance in this instrument will be captured in the model tested, resulting in less residual variance and a smaller residual variance/slope variance ratio. Both are important components of statistical power to detect change in mixed effects models.

For the structural equation model to be tested, the logic of MacCallum, Browne, and Sugawara was followed. This approach allows for the testing of a null hypothesis of not good fit, reversing the role of the null hypothesis

in conventional tests of model fit, so that a significant result provides strong support for good fit. This approach also allows for an estimate of power, where effect size is defined in terms of a null and alternative value of the root mean square error of approximation fit index. Here, adequate power ( $> .98$ ) to reject a hypothesis of close fit ( $RMSEA > .08$ ) with 136 degrees of freedom (a degrees of freedom of 136 is a somewhat conservative estimate as models including more covariates would provide more degrees of freedom), given a population  $RMSEA$  of  $.05$  was obtained. That is, if the true value of  $RMSEA = .08$ , and we test the hypothesis that  $RMSEA \leq .05$ , power is  $> .98$  for rejecting the hypothesis of close fit in the population. Additionally, adequate power ( $.98$ ) to reject a hypothesis of not-close fit ( $RMSEA \geq .05$ ) was also obtained. If model fit is actually extremely good ( $RMSEA < .01$ ), and we test the hypothesis that fit is not close, we have over  $.95$  power to reject the null hypothesis that  $RMSEA \geq .05$ .

With respect to Exploratory Aims, the number of participants likely to complete CBT-I represent a considerable sample with which to conduct fidelity assessments and to identify qualitative themes and the overall sample size offers the ability to explore quantitative data related to participant attitudes.

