Type 1 Error Protection. To help control for Type 1 error, the Benjamini-Hochberg (BH) method will be used to adjust for the multiple comparisons proposed in the current study. The BH method adjusts for multiple comparisons by controlling false discovery rate instead of family-wise error rate. It is less conservative than the more traditional Bonferonni methods, yet still provides adequate protection against Type 1 error. Since its inception, there has been growing evidence suggesting that the false discovery rate based BH method is the optimal solution to the multiple comparison problem in most practical situations.

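### The stated .80 power for suicidal ideation assumes an unadjusted .05, but Benjamini-Hochberg, with no stated family or q, will judge that outcome

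*Combined protocol and SAP*

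**What the plan says.** Under Data Analysis and Statistical Considerations, the Power Analysis paragraph sizes each outcome separately, "using a two-sided alpha of .05 and .80 power". It introduces the four Aim 1 outcomes as "the primary outcomes of interest; insomnia, depression, PTSD, and SI severity", then singles out SI: "For the main outcome of SI, pilot data using the C-SSRS suggests an intercept variance of 10". The result for SI is "With these estimates, 240 participants are required to achieve .80 power". The other three outcomes need fewer: "N = 223 for depression, N = 222, for insomnia, and N= 184 for PTSD". No multiplicity allowance appears in this calculation.

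The Type 1 Error Protection paragraph states that "the Benjamini-Hochberg (BH) method will be used to adjust for the multiple comparisons proposed in the current study". It explains that the method controls the false discovery rate and is less conservative than Bonferroni. It names no family, gives no q, and does not set SI apart.

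The Aim 2 part of Data Analysis gives nine indirect effects and a total effect their own criterion, namely whether 95% limits exclude zero, and does not mention Benjamini-Hochberg (BH). Specific Aims adds association hypotheses 2b to 2d, for example "Depression at 3 months will be positively related to SI at 6 months". Two treatment-attitude instruments are tested under the Exploratory Aims.

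**The concern.** The sample size and the decision rule use different significance thresholds. SI set the sample size, and hypothesis 1d is the suicide-prevention claim, so its power should be stated under the rule that will judge it.

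Under BH the p-value at which SI is declared depends on how many tests are in the family, on q, and on how many of the other tests reject. With four tests at q = .05, an SI p-value between .0125 and .05 may or may not count as significant. If family and q are left unwritten, they could be settled after the results are seen, and that choice could decide the SI claim.

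**Working it through.** **1. Reproducing N = 240.** From the Power Analysis paragraph: intercept variance 10, slope variance 1.2, residual variance 24, no intercept-slope correlation, an effect of .4 at week 30, two-sided .05, power .80, and losses of 7, 5, 3, 3 and 2%. Retention is therefore 1, .93, .88, .85, .82, .80. The text gives neither the time coding nor the SD to which .4 refers. I assumed visits coded 0 to 5 and the model SD at week 30.

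- SD at week 30 = √(10 + 25 × 1.2 + 24) = √64 = 8.0. The difference is .4 × 8.0 = 3.2, or .64 per visit.
- Linear contrast c = t − 2.5, with Σc² = 17.5, so c′μ = .64 × 17.5 = 11.2.
- N = 4(1.960 + .842)² × c′Vc / (c′μ)².
- Without attrition, c′Vc = 1.2 × 17.5² + 24 × 17.5 = 787.5, so N = 197.
- With V scaled for retention, c′Vc = 938.3, so N = 235, about 2% below 240.

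Other codings at the week-30 SD give 239 (months) and 246 (weeks). Visit coding with the baseline SD gives 442 and does not reproduce 240. The reproduction is thus not unique, but it agrees with the text that .80 at N = 240 belongs to an unadjusted .05.

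**2. Design z-values at N = 240.** For SI: 1.960 + .842 = 2.80. For the others: 2.80 × √(240 / stated N).

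| Outcome | Stated N | Mean z | Unadjusted power |
|---|---|---|---|
| SI | 240 | 2.80 | .80 |
| Depression | 223 | 2.91 | .83 |
| Insomnia | 222 | 2.91 | .83 |
| PTSD | 184 | 3.20 | .89 |

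**3. Bounds under BH, assuming four tests and q = .05.** The ordered p-values are compared with .0125, .025, .0375 and .05. SI can never be declared with p above .05, so its power cannot exceed .80. It is always declared with p ≤ .0125 (critical z 2.498), so its power is at least Φ(2.802 − 2.498) = .619.

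**4. Simulated SI power.** BH was applied to simulated z-vectors with a common correlation of 0, .3 or .5 between outcomes.

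| Effects on the other three outcomes | q = .05 | q = .10 |
|---|---|---|
| All as planned | .781, .773, .769 | .867, .860, .856 |
| Insomnia and depression as planned, PTSD null | .742, .734, .731 | not run |
| Insomnia and depression strong (z = 6), PTSD null | .767, .766, .766 | not run |
| Insomnia and depression strong, PTSD as planned | .796, .794, .795 | not run |
| All three strong | .800 | not run |
| All three null (only SI has an effect) | .627, .625, .623 | .726, .725, .723 |

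**5. False SI claims when SI is null.** With the other three as planned or strong, SI is declared in .039-.050 of trials at q = .05 and in .087-.100 at q = .10. The extra power at q = .10 is bought with about twice the false-positive rate on SI.

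**The case against.** **The loss is small on the plan's own terms.** With all effects as planned it is 2-3 points. The stated .80 is itself uncertain by about that much: a generalised least squares version of the step 1 calculation gives .813 at N = 240, and BH on four outcomes then gives SI power of about .78-.80. The protocol also expects a gain from the new instrument: "For the main SI outcome, power likely improves with the change to the SSI". This stands as a reason for moderate weight. It does not remove the mismatch, because the protocol puts no figure on the gain and does not link it to BH.

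**Insomnia and depression are likely to reject easily.** Their pilot effects were very large, but the pilot compared CBT-I with treatment as usual, not sleep hygiene. Even with both at z = 6, a null PTSD effect leaves SI at about .77.

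**Stronger readings that a reader might infer.** The first is that BH spans every test in the document, so that SI power falls far below the figures above. Four Aim 1 tests, nine indirect effects, the total effect and five paths in 2b to 2d make 19. The documents do not support this as the natural reading: the indirect and total effects have their own criterion, and the attitude tests are exploratory. The lowest figures for such a family also require the total effect on 6-month SI to be null while SI keeps its planned effect at that same visit, which is incoherent. Giving only that test an effect yields .57-.58 for 19 tests; making the five associations strong as well (z = 6, assumed) yields about .70-.71.

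The second is that the trial must be enlarged. About 341 participants would restore .80 at the strictest step, .0125, but BH applies that step to SI only when none of the other three outcomes is also declared significant.

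The third is that writing the family and q would fix SI's threshold. It would not: with four tests at q = .05 the threshold still runs from .0125 to .05 with the other outcomes. The plan also keeps quadratic and piecewise alternatives to the linear SI model open.

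**Conclusion.** The point holds as a mismatch between the power statement and the decision rule. Under q = .05 and a family of four, .80 is a ceiling for SI, reached only when the other three outcomes practically always reject. The planned case is 2-3 points lower and the extreme case about 17-18 points lower. At q = .10 the planned case would instead lie above .80.

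These figures rest on the stated .80 as the unadjusted power, on q and the family (neither is in the documents), and on correlations of 0 to .5 between the outcome statistics. The documents do not show that the trial is too small, and N = 240 need not change. The Aim 2 conflict between 95% limits and BH is a separate matter. It affects SI's power only if those tests share SI's family.

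**What to change.** 1. In Type 1 Error Protection, state that the BH family containing SI is the four Aim 1 outcomes at q = .05, and that the Aim 2 and attitude tests lie outside it.
2. In the Power Analysis paragraph, restate SI power at N = 240 as about .77-.78 with all four effects as planned, ranging from .62 to .80 with the other outcomes.
3. In the Aim 2 analysis text, say whether the 95% limits or a BH-adjusted result decides the indirect and total effects. If BH is to apply to Aim 2, give those tests their own family and q.

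The cost is wording and a stated SI power 2-3 points lower. No participants are added.

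An option the sponsor may prefer is to test SI alone at two-sided .05 and apply BH at q = .05 to hypotheses 1a to 1c. SI keeps .80. With effects as planned, insomnia and depression have .80-.82 and PTSD .86-.88; insomnia and depression fall to about .76-.77 if PTSD is null. The price is that 1a to 1c become secondary, although the protocol calls all four primary, and that error is not jointly controlled across the four. For example, if all four were null and independent, the chance of at least one false claim would be 1 − .95 × .95 = .0975.
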